### **8.1.2 Methods of Measurement**

Every attempt should be made to image each patient using an identical acquisition protocol on the same scanner for all imaging time points. Tumor measurements should be made by the same investigator or radiologist for each assessment whenever possible. Change in tumor measurements and tumor response to guide ongoing study treatment decisions will be assessed by the investigator.

Bone scan or PET scan is not adequate for assessment of RECIST v1.1 response in target lesions. In selected circumstances where such modalities are the sole modality used to assess certain nontarget organs, those non-target organs may be evaluated less frequently. For example, bone scans may need to be repeated only when complete response is identified in target disease or when progression in bone is suspected.

Bone scans may be collected per local standards, as clinically indicated.

Screening assessments are to be performed within 28 days prior to treatment assignment. In addition to the chest, abdomen, pelvis, and brain (if brain metastases are suspected at baseline), all known sites of disease should be assessed at baseline. Subsequent assessments should include chest, abdomen, pelvis, and all known sites of disease using the same imaging method and technique as was used at baseline.

In addition, subjects receiving study treatment beyond progression must continue tumor assessments until such treatment has been discontinued. Treatment beyond disease progression is detailed in Section [4.3](#).

### **8.2 Informed Consent, Screening, and Enrollment**

Patients must be able to provide written informed consent and meet all eligibility criteria prior to enrollment.

Only patients who meet all eligibility criteria outlined in Section [5.0](#) will be enrolled in this study. No waivers of inclusion or exclusion criteria will be granted by the Investigator and Sponsor or its designee for any patient enrolled in the study. Patients who qualify for Phase 1a of the study will be enrolled into the first available cohort. A patient may be enrolled into either Phase 1a or Phase 1b of the study, but not both.

### **8.3 Safety Assessments**

Planned time points for all safety assessments are provided in the Schedule of Assessments.

Only data for the procedures and assessments specified in this protocol should be submitted to the Sponsor on eCRF. Additional procedures and assessments may be performed as part of standard of care; however, data for these assessments should remain in the patient's medical record and should not be provided to the Sponsor, unless specifically requested.

#### **8.3.1 Medical History and Demographics**

Patient medical and surgical history includes a thorough review of significant past medical and surgical history, current conditions, concomitant therapies, alcohol and smoking history, and smoking status. Demographics including age, gender, race, and ethnicity will be recorded.

#### **8.3.2 Physical Examinations**

A complete physical examination including height and weight will be performed at screening. A limited physical examination (eg, symptom-directed examination of specific organ systems/ body area) should be conducted at the specified time points after screening in accordance with the Schedule of Assessments. Investigators should pay special attention to clinical signs related to previous serious illnesses.

#### **8.3.3 Vital Signs**

Temperature, pulse rate, respiratory rate, and blood pressure will be assessed.

Blood pressure and pulse measurements should be preceded by at least 5 minutes of rest for the patient in a quiet setting.

#### **8.3.4 Electrocardiograms**

Twelve-lead ECG will be obtained as outlined in the Schedule of Assessments. ECGs for each patient should be obtained from the same machine whenever possible. To minimize variability, it is important that patients be in a resting position for at least 5 minutes prior to each ECG evaluation. Body position should be consistently maintained for each ECG evaluation to prevent changes in heart rate. Environmental distractions (e.g., television, radio, conversation) should be avoided during the pre-ECG resting period and during ECG recording.

The exact time of ECG should be recorded. The ECGs should be reviewed promptly by a qualified physician and any clinically important finding should be recorded on the appropriate eCRF. The Investigator is responsible for providing the interpretation of all ECGs. The results will include heart rate, PR interval, QRS interval, QT interval, and QTc interval.

Additional ECGs may be obtained at any time if clinically indicated. If abnormal (excluding sinus tachycardia), ECGs should be obtained as clinically indicated until the abnormality is

resolved or clinically stable. Any clinically significant changes in ECG that occur during the study should be reported as an AE in the eCRF.

### **8.3.5      Eastern Cooperative Oncology Group Performance Status**

ECOG performance status will be assessed in all patients in accordance with the Schedule of Assessments. The ECOG performance scale is provided in [Appendix 5](#). The ECOG performance status is a scale used to assess how a patient's disease is progressing, assess how the disease affects the daily living abilities of the patient, and determine appropriate treatment and prognosis.

### **8.3.6      Clinical Safety Laboratory Assessments**

See [Appendix 1](#) for the list of clinical laboratory tests to be performed and the Schedule of Assessments for the timing and frequency.

The investigator must review the laboratory report, document this review, and record any clinically relevant changes occurring during the study in the AE section of the eCRF. The laboratory reports must be filed with the source documents.

All laboratory tests with values considered clinically significantly abnormal during participation in the study should be repeated until the values return to normal or baseline or are no longer considered clinically significant by the investigator or medical monitor.

All protocol-required laboratory assessments, as defined in [Appendix 1](#), must be conducted in accordance with the laboratory manual and the Schedule of Assessments.

If laboratory values from non-protocol specified laboratory assessments performed at the institution's local laboratory require a change in patient management or are considered clinically significant by the investigator (eg, SAE or AE or dose modification), then the results must be recorded in the eCRF.

## **8.4      Adverse Events and Serious Adverse Events**

The definitions of an AE or SAE can be found in [Appendix 2](#).

Assessment of AEs will follow the guidelines provided in the NCI CTCAE version 4.03.

Abnormal laboratory results that lead to a change in patient treatment management (e.g., dose delay, requirement for additional medication or monitoring) are considered clinically significant for the purposes of this study and will be recorded on the AE page of the eCRF.

AEs will be reported by the patient (or, when appropriate, by a caregiver, surrogate, or the patient's legally authorized representative).

The investigator and any designees are responsible for detecting, documenting, and recording events that meet the definition of an AE or SAE and remain responsible for following up AEs to resolution.

#### **8.4.1 Time Period and Frequency for Collecting AE and SAE Information**

All SAEs will be collected from the start of study treatment (Cycle 1 Day 1). In addition, any SAE occurring between signing of ICF and start of treatment will be recorded if it is due to a study related procedure. The SAEs will be collected through the Day 100 EOT visit.

All AEs will be collected from the start of study treatment (Cycle 1 Day 1) through completion of study, at the time points specified in the Schedule of Assessments. AEs ascribed to study treatment and SAEs should be assessed through the Day 100 EOT visit.

Medical occurrences that begin before the start of study treatment but after obtaining informed consent will be recorded on the Medical History section of the eCRF, not the AE section, unless they directly correlate to a study-related procedure, in which case they will be reported on the AE eCRF page.

All SAEs will be recorded and reported to the sponsor or designee within 24 hours, as indicated in [Appendix 2](#). The investigator will submit any updated SAE data to the sponsor or designee within 24 hours of it being available.

SAEs occurring after the Day 100 EOT visit should be reported to the Sponsor by the Investigator only if the Investigator considers the event reasonable related to FPT155. SAEs should always be recorded on the AE eCRF.

Investigators are not obligated to actively seek AE or SAE in former study patients. However, if the investigator learns of any SAE, including a death, at any time after a patient has been discharged from the study, and he/she considers the event to be reasonably related to the study treatment or study participation, the investigator must promptly notify the sponsor.

The method of recording, evaluating, and assessing causality of AE and SAE and the procedures for completing and transmitting SAE reports are provided in [Appendix 2](#).

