**Table 2: Schedule of Assessments –Dose Exploration/Expansion (monotherapy and FPT155 + pembrolizumab) (Contd)**

Study Phase	Screening	Cycle 1 (21 Days)					Subsequent Cycles* (21 Days)	EOT Follow-Up	LTFU	
Cycle Day	Screening	D1	D2	D4	D8	D15	D1	28- and 100- Days Post Last Dose		
Window (Days)	-28			± 1	± 1	± 1	± 3	± 7	± 14	Notes
Vital Signs	X	X	X	X	X	X	X	X		Vital signs include blood pressure, respiratory rate, pulse and temperature. For the first and second infusions of FPT155, measure vital signs prior to dosing, every 15 minutes during the infusion, and after completion of each FPT155 IV infusion at the following timepoints: 5 minutes, 15 minutes, 30 minutes, 1 hour, 2 hours, 3 hours, 4 hours, 5 hours, and 6 hours post-dose. For all subsequent infusions, measure vital signs prior to dosing, every 15 minutes during the infusion, and after completion of each FPT155 IV infusion. Additional vital signs may be performed as clinically indicated.
12-Lead ECG	X	X						X		ECG is required at screening, pre-dose on Cycle 1 Day 1, and at the EOT visits. Additional ECGs may be obtained at any time if clinically indicated.
ECOG Performance Status	X	X					X	X		
Prior / Concomitant Medications		←————→								
Adverse Events Review		←————→								AEs will be assessed before and after study drug dosing on applicable visits. AEs ascribed to study drug and SAEs should be assessed through the Day 100 EOT visit.

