6.3.1 Adverse Event

All AEs were collected from the start of study treatment (Cycle 1 Day 1) through completion of study, at the time points specified in the [Appendix 1](#) and [Appendix 2](#).

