6.3.1.5 Treatment-Emergent Adverse Events (TEAE)

A treatment-emergent AE (TEAE) is defined as an AE that was not present prior to the start date of study drug or was worsened during treatment and 100 days after last dose of treatment. An AE

that was present at treatment initiation but resolved and then reappeared and the event severity increase while the subject was on treatment is also a TEAE.

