6.3.1.6 Summary of Adverse Events and Deaths

An overall summary of TEAEs will summarize the number (%) of patients by the treatment group and overall with: all TEAEs, TEAEs with grade 3 or higher, TEAEs related to FPT155-001, TEAEs related to FPT155-001 with grade 3 or higher, TEAEs leading to study drug discontinuation, serious TEAEs, serious TEAEs related to FPT155-001, TEAEs leading to death. For the Phase 1a Combination Dose Escalation/Exploration, the TEAEs related to pembrolizumab, TEAEs related to pembrolizumab with grade 3 or higher and serious TEAEs related to pembrolizumab will also be included in the overall summary table.

The number and percentage of subjects who experienced at least 1 TEAE will be provided and summarized by SOC, PT, maximum severity, and treatment group. AEs will be summarized in alphabetic order of SOC and then by PT in descending order of total frequency within each SOC. For summaries by severity, the maximum severity will be used for those AEs that occurred more than once in a subject. A subject with multiple adverse events within a SOC is only counted once in this SOC. Similarly, a subject with multiple adverse events within a PT is only counted once in this PT.

- TEAEs
- TEAEs with grade 3 or higher
- TEAEs related to FPT155
- TEAEs related to pembrolizumab (for Phase 1a Combination Dose Escalation/Exploration only)
- TEAEs leading to drug discontinuation of FPT155
- TEAEs leading to drug discontinuation of pembrolizumab (for Phase 1a Combination Dose Escalation/Exploration only)
- Serious TEAEs
- Serious TEAEs related to FPT155
- Serious TEAEs related to pembrolizumab (for Phase 1a Combination Dose Escalation/Exploration only)
- TEAEs leading to death

In addition to the above summary tables, TEAEs will be summarized by PT only in descending order of total frequency.

All AE and recorded deaths for the safety population will be listed.

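### Protocol 8.4.1 gives two adverse event collection rules that disagree, and the SAP's 100-day all-cause TEAE tables are complete only if the broader rule is followed

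*Protocol*

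**What the plan says.** Protocol 8.4.1 contains two consecutive sentences of different scope. The broad one reads "All AEs will be collected from the start of study treatment (Cycle 1 Day 1) through completion of study", and adds that this happens "at the time points specified in the Schedule of Assessments". The narrow one reads "AEs ascribed to study treatment and SAEs should be assessed through the Day 100 EOT visit". The same section collects all SAEs to the Day 100 visit and, after that visit, asks for an SAE report only where the investigator considers the event related.

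The Schedule of Assessments, to which the broad sentence defers, carries the narrow rule in its AE notes. Protocol Table 2 says "AEs ascribed to study drug and SAEs should be assessed through the Day 100 EOT visit". Table 1 and SAP Appendices 1 and 2 have the same sentence.

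SAP 6.3.1 repeats the broad rule in the past tense: "All AEs were collected from the start of study treatment (Cycle 1 Day 1) through completion of study". SAP 6.3.1.5 defines a TEAE as an AE that was not there before study drug started or that "was worsened during treatment and 100 days after last dose of treatment". It sets no condition on attribution. SAP 6.3.1.6 then plans counts of "all TEAEs, TEAEs with grade 3 or higher, TEAEs related to FPT155-001", so all-cause and related events are reported side by side.

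Protocol 4.4 ends the study at the Day 100 visit in Phase 1a. In Phase 1b the study ends when survival follow-up ends for the last patient, or when the sponsor terminates the study.

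**The concern.** The incidence of AEs is a primary endpoint in all three sets of objectives in Protocol 3.0, and the SAP reports it whatever the attribution. A table of that kind needs every AE in its window to be recorded, whatever the investigator thinks of its cause. If recording after treatment depends on causality, the all-cause count loses events, the related share looks larger than it is, and ascertainment can differ between sites.

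Attribution deserves care in a first-in-human immune agonist. Protocol 2.4 expects delayed immune-mediated toxicity, and Appendix 2 sets a fairly demanding causality test: there must be positive grounds for a causal link, and being unable to exclude one is not enough. A late non-serious event of uncertain cause could therefore be judged unrelated and, under the narrow rule, never entered. It could not be re-examined later if a pattern emerged. The SAP 6.3.1.3 rule that counts missing causality as related helps only events that were recorded.

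**Working it through.** The plan gives no figure to reproduce here, so the check sets the texts side by side and then does simple window arithmetic.

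| Place | Which AEs | Until when |
|---|---|---|
| Protocol 8.4.1, broad sentence | all | completion of study, at Schedule time points |
| Protocol 8.4.1, narrow sentence | treatment-ascribed AEs, and SAEs | Day 100 visit |
| AE notes, Protocol Tables 1 and 2, SAP Appendices 1 and 2 | drug-ascribed AEs, and SAEs | Day 100 visit; end date for other AEs not stated |
| SAP 6.3.1 | all | completion of study, at Appendix 1 and 2 time points |
| SAP 6.3.1.5 and 6.3.1.6 | TEAEs of any attribution | 100 days after last dose |

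**Reading 1: the broad sentence governs.**
- Phase 1a: completion of study is the Day 100 visit, so collection matches the TEAE window, apart from the ±7-day window on that visit. The narrow sentence then adds nothing; it has an effect only if it restricts.
- Phase 1b: completion of study lies beyond Day 100, in survival follow-up that may be by telephone. Taken literally, non-serious unrelated AEs would be collected for longer than unrelated SAEs, which stop at Day 100. That is unlikely to be intended.

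**Reading 2: sites follow the narrow rule.** Non-serious AEs judged unrelated and arising after treatment may not be recorded, including non-serious events of grade 3 or higher. SAEs and drug-ascribed AEs are still collected to Day 100, and DLTs fall within a 21-day interval.

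**Illustration under Reading 2.** The documents give no stop day for the exposed events, so two assumptions are shown: collection stops at the Day 28 visit, or at the last dose.
- Post-dose days with attribution-dependent collection: 100 − 28 = 72, or 100 − 0 = 100.
- TEAE window with k doses given every 21 days: 21(k − 1) + 100 days.

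| Doses k | Window (days) | Stop at Day 28 | Stop at last dose |
|---|---|---|---|
| 2 | 121 | 72/121 = 60% | 100/121 = 83% |
| 4 | 163 | 72/163 = 44% | 100/163 = 61% |
| 8 | 247 | 72/247 = 29% | 100/247 = 40% |

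Counting the first dosing day as well adds one day to each window and moves the shares by at most about one point. These are shares of time at risk in which recording of one class of event would depend on attribution. They are not estimates of missed events.

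**The case against.** The strongest reply is that nothing in the text says other AEs stop. The narrow sentence can be read as a minimum for two important classes of event, with the broad sentence still in force. Appendix 2 defines an AE irrespective of relationship to treatment, Section 8.4 makes investigators responsible for recording whatever meets that definition, and the first sentence of the schedule note has no attribution limit. The AE row in the tables is drawn as an arrow across the visit columns. Where it ends cannot be read from the text copy and should be checked on the page; it may show AE review at both end-of-treatment visits. In Phase 1a the broad sentence already gives the right window. In Phase 1b, the tie to Schedule time points may limit the open-ended reading in practice. The study is also non-randomised and descriptive, with the same wording applied to every cohort.

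Much of this stands. That the tables exclude other AEs is an inference from what they leave out, and any understatement depends on how sites read them. Even so, an arrow reaching Day 100 would not settle the matter, because the note beside it names only two classes of event for that visit. In Phase 1a the narrow sentence is redundant unless it is meant to restrict, so a site can reasonably take it that way.

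Three stronger conclusions might be drawn, and the documents do not support them:
- That all-cause TEAE rates are in fact understated. This holds only if sites apply the narrow reading.
- That the percentages above measure bias. SAEs and related AEs are still collected throughout that time. A patient with an unrecorded event still counts in the any-TEAE row if another TEAE was recorded; the loss may then be confined to a preferred term or a maximum grade.
- That detection of drug toxicity or the choice of recommended dose is compromised. Related and serious events are collected to Day 100 on either reading. What remains is an immune event wrongly judged unrelated, which is a narrower risk.

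**Conclusion.** The inconsistency is real and should be resolved. Two rules stand next to each other in 8.4.1, the operational tables repeat the narrower one, and the SAP's all-cause tables assume the broader one. The possible consequence is an understated incidence of all-cause TEAEs, confined to non-serious events judged unrelated that arise after treatment. It depends on sites following the narrow rule, and its size cannot be estimated from the documents. The only quantity available is exposure: about 72 of the 100 post-dose days if recording of such events stopped at Day 28, and all 100 if it stopped at the last dose, both being assumptions. The loose grammar of the TEAE definition does not change this. The 100 days may attach only to worsening, leaving new-onset events without a stated end, but neither reading brings in attribution.

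**What to change.** State one rule in Protocol 8.4.1, Protocol Tables 1 and 2, and SAP Appendices 1 and 2: all AEs regardless of causality through the existing Day 100 end-of-treatment visit, and after that only SAEs considered related. This matches the SAP's 100-day window, and the last part is already in 8.4.1. SAP 6.3.1 should drop the reference to completion of study, and 6.3.1.5 should apply the 100-day limit to new-onset and worsened events alike.

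If narrower collection is intended, name its cut-off day, end the all-cause TEAE tables at that day, and report related AEs and SAEs from then to Day 100 in a separate table.

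The cost is wording in the protocol, the CRF completion guidance and the SAP. No visit is added. The downside is some extra AE data entry and possibly slightly higher reported all-cause AE rates.

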## 6.0 STUDY INTERVENTION

Study intervention is defined as any investigational intervention(s), marketed product(s), placebo, or medical device(s) intended to be administered to a study patient according to the study protocol. For patients enrolled for evaluation of FPT155 monotherapy, the study intervention administered is FPT155. For patients enrolled for evaluation of combination treatment, the study interventions administered are FPT155 and pembrolizumab.

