### 6.9.6.2 Pembrolizumab

Dose modifications for pembrolizumab will be allowed in accordance with the local [Keytruda® package insert](#). Dose reductions for pembrolizumab are not permitted.

Pembrolizumab may cause severe or life-threatening infusion-reactions including severe hypersensitivity or anaphylaxis. Signs and symptoms usually develop during or shortly after drug infusion and generally resolve completely within 24 hours of completion of infusion. Dose modification and toxicity management for infusion reactions associated with pembrolizumab should be in accordance with the guidelines provided in the [Keytruda® USPI](#).

AEs associated with pembrolizumab exposure may represent an immunologic etiology. These irAEs may occur shortly after the first dose or several months after the last dose of pembrolizumab treatment and may affect more than one body system simultaneously. irAEs may be managed with interruptions of pembrolizumab, administration of corticosteroids and/or other supportive care. Dose modification and toxicity management for irAEs associated with pembrolizumab should be done in accordance with the guidelines provided in the local Keytruda® package insert.

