### General aspects of irAEs

In general, irAEs occur quite early, mostly within weeks to 3 months after initiation of immune checkpoint blockers. However, the first onset of irAEs has been documented as long as 1 year after discontinuation of treatment.

The role of tissue biopsy in the diagnosis of immune-therapy related toxicity is not established. Some recommendations suggest tissue biopsy in higher grade (3 and 4) toxicity [skin, gastrointestinal (GI), liver, kidney, lung] where there is diagnostic doubt about the aetiology of the complication and management would be altered by the outcome of the biopsy procedure [15]. In

general, when biopsy is carried out in such circumstances, the reporting pathologist must be apprised of the specific reasons for the biopsy procedure.

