6.3.2 Deaths

All deaths during the study, deaths within 28 days after the last dose of treatment, deaths within 100 days after the last dose of treatment and deaths beyond 100 days after the last dose of treatment will be summarized, the cause of deaths will also be included. All recorded deaths for safety population will be listed.

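### Section 8.4.1 gives two conflicting rules for SAEs after Day 100, and in combination patients they give opposite instructions for an event attributed to pembrolizumab alone

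*Protocol*

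**What the plan says.** Protocol 8.4.1 collects SAEs through the Day 100 end-of-treatment visit. SAEs after that visit "should be reported to the Sponsor by the Investigator only if the Investigator considers the event reasonable related to FPT155". The sentence that follows adds: "SAEs should always be recorded on the AE eCRF".

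The next paragraph of 8.4.1 says "Investigators are not obligated to actively seek AE or SAE in former study patients". It then adds that if the investigator learns of any SAE after a patient has been discharged, and "he/she considers the event to be reasonably related to the study treatment or study participation, the investigator must promptly notify the sponsor".

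Protocol 6.0 fixes what was given: "For patients enrolled for evaluation of combination treatment, the study interventions administered are FPT155 and pembrolizumab". On timing, Protocol 6.9.6.2 says of pembrolizumab: "These irAEs may occur shortly after the first dose or several months after the last dose of pembrolizumab treatment".

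SAP 6.3.1.3 counts an AE as treatment-related if the investigator attributes it to either drug. SAP 6.3.1.5 defines treatment-emergent events with a 100-day window after the last dose, and every SAE table in SAP 6.3.1.6 is built on treatment-emergent events. SAP 6.3.1.6 also lists all AEs. SAP 6.3.2 says that "deaths beyond 100 days after the last dose of treatment will be summarized", with cause.

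**The concern.** Delayed immune toxicity is the kind of harm most likely to appear after scheduled safety collection has ended. From that point the sponsor depends on what sites choose to report, so the rule they follow has to be unambiguous. Here one sentence sets an exclusive condition tied to FPT155, and the next paragraph imposes a duty that extends to pembrolizumab. A site with a combination patient who has a late serious event blamed on pembrolizumab can find support in the text for either course. If it follows the narrower sentence, the sponsor may not be notified of an event that bears directly on the safety of the combination.

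The analysis side raises a smaller question. If late related SAEs do reach the database, it is not clear that any planned SAE table counts them.

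**Working it through.** No power, alpha or event count bears on this point. The check sets the provisions side by side.

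**1. Do the two rules cover the same patients and the same time?** Yes, for the combination. It exists only in Phase 1a, and Protocol 4.4 makes the Day 100 visit the end of study in Phase 1a. After Day 100 and after discharge are therefore the same period. One loose end is that Protocol 8.1.1 continues scans every 12 weeks in patients who stop treatment without progression. A site could regard such a patient as not yet discharged, and the narrower sentence would then stand alone.

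**2. What does each rule require?**

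| Investigator's attribution | Post-Day-100 sentence | Next paragraph |
|---|---|---|
| FPT155, alone or with pembrolizumab | report | notify |
| Pembrolizumab alone (combination only) | do not report | notify |
| Study participation only | do not report | notify |
| None of these | do not report | no duty |

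The second row is the substantive conflict. The third row is a smaller mismatch in scope that does not depend on the drug.

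**3. How many patients?** The planned total reproduces: 58 + 50 + 240 + 30 + 30 = 408 (Protocol 9.2). Combination patients: 30 + 30 = 60. Share: 60 / 408 = 14.7%. For the other 348, FPT155 is the only study drug, so the drug wording gives the same answer under both rules.

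**4. Is a late event attributed to pembrolizumab alone plausible?** Yes, from 6.9.6.2. In addition, Protocol 4.2 allows one drug to continue alone for as long as 12 more months after the other stops. The synopsis counts the follow-up visits from the last dose of any study drug. If pembrolizumab is the drug that continues, Day 100 can fall about 365 + 100 = 465 days after the last FPT155 dose (taking 12 months as 365 days), when attribution to FPT155 is least likely.

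**5. How late can onset be?** The guideline reproduced in Protocol Appendix 9 says "the first onset of irAEs has been documented as long as 1 year after discontinuation of treatment". That is 365 − 100 = 265 days beyond the Day 100 visit. It is an outer bound, because the same paragraph places most such events within weeks to 3 months of starting treatment.

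**6. Where do late related SAEs go in the analysis?** The treatment-emergent definition in SAP 6.3.1.5 can be read in two ways:
- The 100 days limits both new and worsened events. This is the usual reading. A new SAE on, say, day 150 is not treatment-emergent and enters no SAE table.
- The 100 days limits only worsening of events already present. The same SAE is then treatment-emergent and is tabulated.

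On the first reading, a late fatal event still enters the deaths summary with cause, though not by relatedness, and a late non-fatal one appears only in the AE listing. Protocol Table 12 plans SAE incidence with no treatment-emergent limit, so the restriction comes from the SAP. The Day 100 visit may also fall on days 93 to 107 (100 ± 7), so the collection cut-off and the table cut-off can differ by up to 7 days either way.

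**The case against.** The strongest reply is that this is a slip of wording with little practical effect. The next paragraph is mandatory and covers these patients. SAEs are always to go on the AE eCRF. Protocol Appendix 2 asks for SAE information to be entered and sent within 24 hours, with no limit by drug. A site would have to follow one sentence and overlook three other provisions. This stands as mitigation, and it is why non-reporting is a possibility and not the expected outcome. It does not remove the conflict: the narrower sentence is worded as an exclusive condition, and recording on the eCRF is not the same instruction as notifying the sponsor.

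A reader might also infer that a patient continuing pembrolizumab alone drops out of SAE collection once FPT155 stops. The protocol does not support that. Its Tables 1 and 2 start the follow-up visits only when all study treatment has been discontinued, so full collection runs to about 100 days after the last pembrolizumab dose. (SAP Appendix 2 words the trigger as discontinuation of FPT155, but the protocol governs conduct.)

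On tabulation, the reply is that a listing is a defensible place for events nobody is obliged to seek, since a rate from passive reports would under-count against a full denominator. That stands, and it makes the extra count optional. Nor can it be said that late toxicity is ignored when the regimen is judged: under Protocol 4.1.1.1 and 4.1.1.6 the Cohort Review Committee reviews cumulative safety and the recommended dose takes account of toxicity beyond the DLT period.

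**Conclusion.** The contradiction in 8.4.1 is real and should be reconciled. Its reach is limited to at most about 60 of 408 planned patients (14.7%), and within them to SAEs after Day 100 attributed to pembrolizumab and not to FPT155. The documents give no basis for estimating how many such events would occur. The conclusion assumes that study treatment in 8.4.1 has the meaning given to study intervention in Protocol 6.0.

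Three stronger readings are not supported:
- That late pembrolizumab SAEs will go unreported. The adjoining provisions all point towards reporting.
- That 265 days measures the gap. It is the distance to the latest onset cited for checkpoint blockers in general, not a typical delay.
- That late related SAEs have no planned output. Late deaths are summarised with cause and all AEs are listed. What can be said is that non-fatal related SAEs with onset more than 100 days after the last dose are, on the usual reading, listed but not tabulated.

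The reporting conflict merits correction at the next amendment. The tabulation point is secondary.

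**What to change.** **Protocol 8.4.1.** Reconcile the post-Day-100 sentence with the paragraph after it so that both use the same relatedness scope. To agree with SAP 6.3.1.3 the scope would name FPT155 or pembrolizumab, and to agree with the next paragraph it would also cover study participation. Substituting a phrase for study drug alone would leave the second mismatch in place. It would help to state in the same place whether a Phase 1a patient still having scans after Day 100 counts as discharged.

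**SAP 6.3.1.5.** State whether the 100 days applies to new events, to worsened events, or to both.

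**SAP 6.3.1.6 (optional).** Add a short count of related SAEs with onset more than 100 days after the last dose, by drug, group and dose, labelled as passively reported, next to the existing summary of deaths beyond 100 days.

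The cost is a sentence in the protocol, a clarified definition in the SAP and, if wanted, one small table. No visits or procedures are added. Sites may submit a few more SAE reports.
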